6.1.5 Clinically Evaluable (CE) Populations

Two CE analysis sets will be defined; the CE-EOT and the CE-PTE. To be included in the CE-EOT and the CE-PTE populations, subjects must be in the mITT population. Subjects will be *included* in or *excluded* from the CE analysis sets based on the additional criteria listed below.

6.1.5.1 Diagnosis of ABSSI

To be included in the CE-EOT and CE-PTE populations, subjects must meet the following protocol defined inclusion criteria that describe the ABSSI:

Inclusion Criterion 3: Has a qualifying skin and skin structure infection. All qualifying lesions must be greater than or equal to 75 cm² in total surface area of contiguous involved tissue, calculated as the product of the maximum length (head-to-toe) multiplied by the maximum width (measured perpendicular to length) as measured by the investigator using a wound ruler. Involved tissue is defined as tissue exhibiting clear evidence of one or more of the following: erythema, edema, or induration.

The classification of qualifying infections is shown below:

- a. Wound infection – an infection characterized by purulent drainage from a wound with surrounding erythema, edema, and/or induration extending at least 5 cm in the shortest distance from the peripheral margin of the wound.
- b. Cellulitis/erysipelas – a diffuse skin infection characterized by spreading areas of erythema, edema, and/or induration.
- c. Major abscess – an infection characterized by a collection of pus within the dermis or deeper that is accompanied by erythema, edema and/or induration extending at least 5 cm of in the shortest distance from the peripheral margin of the abscess.

Inclusion Criterion 4: Has evidence of a systemic inflammatory response within the 24 hours prior to randomization, as indicated by ONE of the following:

- a. Elevated white blood cell (WBC) count (greater or equal to 10,000 cells/mm³) or leukopenia (less than or equal to 4,000 cells/mm³)
- b. Elevated immature neutrophils (greater than or equal to 15% band forms) regardless of total peripheral WBC count
- c. Lymphatic involvement: lymphangitis or lymphadenopathy that is proximal to and in a location that suggests drainage from the qualifying infection
- d. Fever or hypothermia documented by the investigator (temperature greater than 38.0°C [100.4°F] or less than 36.0°C [95.5°F])

6.1.5.2 Prior Antibiotic Therapy

Subjects will be excluded from the CE populations if they meet either of the prior antibiotic exclusion criteria:

Exclusion Criterion 1: Has received 1 or more doses of a potentially effective systemic antibacterial treatment within the 72-hour period prior to randomization (a subject will be considered to have received a potentially effective systemic antibacterial treatment if the pathogen identified as causing the infection is shown to be susceptible to the antibacterial treatment given or, in the circumstance where a pathogen is not identified, if the antibacterial agent is approved for treatment of skin infections or is known to have activity against any of the leading Gram-positive causes of ABSSSI (eg, *Staphylococcus aureus*, *Streptococcus* species [spp.], *Enterococcus* spp.]). EXCEPTION: Subjects may be eligible despite prior antibacterial therapy if they have been treated with a single dose of a short-acting, non-oxazolidinone antibacterial (ie, an antibacterial whose standard dosing regimen is more frequent than once per day, see list in [Appendix 1](#) of the protocol).

Exclusion Criterion 2: Has, for any reason, used a topical antibacterial agent(s) with specific antibacterial activity (eg, mupirocin, retapamulin, fusidic acid) continuously within the 72-hour period prior to first dose of test article, if applied to the skin for greater than or equal to 72 hours.

6.1.5.3 Concomitant Antibiotic Therapy

Subjects who receive any systemic concomitant antibiotic therapy from the first dose of test article through the EOT visit and through the PTE visit with a spectrum of activity against the known or potential Gram-positive infecting pathogen(s) responsible for the infection under study will be excluded from the CE-EOT and CE-PTE populations, respectively, unless the subject receives the antibiotic therapy for treatment of the ABSSSI due to insufficient therapeutic effect of the test article.

Subjects who receive a systemic concomitant antibiotic that is not effective against the Gram-positive baseline pathogen, or if no Gram-positive pathogen is isolated and the antibiotic does not have Gram-positive activity, will be included in the CE-EOT and CE-PTE populations.

In addition, subjects who have any topical antibacterial agent applied to the infection site (except for antibiotic/antiseptic-coated dressing applied to the clean postsurgical wound) with a spectrum

that is active against the known or potential infecting pathogen(s) responsible for the infection under study from the first dose of test article through the EOT or PTE visits, will be excluded from the CE-EOT and CE-PTE populations, respectively.

Antimicrobials that will not interfere with the course of the ABSSSI are allowed and do not affect inclusion in the CE populations, eg, metronidazole, norfloxacin, nalidixic acid, piperacillin sodium, oral vancomycin, antifungals, antivirals or topical antibiotics used for decontamination or in places other than the primary lesion.

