- ⁿ Blood pressure and pulse rate should be measured within 30 min before, and approximately (\pm 15 minutes) 1 hour after and 3 hours after the completion of the odd numbered doses on Days 2 and 3. In the event that the subject takes the dose before arriving for the office visit, the site should collect the 1 and 3 hour post dose measurements if possible, if not then a single measurement should be made at any time during the visit and the date and time recorded.
- ^o A 12-lead ECG should be performed at screening, at the EOT visit, and as otherwise clinically indicated.
- ^p A urine dipstick test will be performed locally at Screening.
- ^q All women will have a local urine or serum pregnancy test at Screening.
- ^r All women will have blood collected for a serum β -hCG pregnancy test at the Central Laboratory at the Screening, EOT and PTE visits.
- ^s Blood will be collected for hematology (includes coagulation) and serum chemistry testing at the Central Laboratory at Screening and at the Day 3, Day 7, Day 10, EOT and PTE visits.
- ^t At the Screening visit, blood will be collected for local laboratory hematology and serum chemistry evaluations required for assessing subject eligibility.
- ^u If bacteria are isolated from blood cultures, repeat blood cultures should be collected. If subsequent blood cultures are also positive, repeat the blood cultures as necessary until negative blood cultures are obtained.
- ^v At the EOT and/or PTE visit, blood cultures and infection site specimen cultures and Gram stains should be obtained only for subjects who are clinical failures and require alternative antibacterial treatment for the infection under study.
- ^w A subject's AEs and SAEs will be recorded and reported from signing of the ICF to the Final Follow-up assessment.
- ^x A 6 hour fast is required before and a 2 hour fast is required following all odd numbered doses. The total duration of test article therapy for all subjects will be 7 to 14 days. Test article may be dispensed and reconciled by blinded personnel. Subjects will be asked to return all unused test article and packaging at each visit. At the EOT visit subjects will return the test article packaging and site staff will perform accountability.
- ^y Subjects should receive their first dose of test article at the site within 4 hours after randomization.
- ^z Subjects should be instructed not to take the odd numbered dose on Day 2 until they return to the site for the Day 2 visit.

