13.1 Prohibited Treatment

- Use of all non-study investigational medications or devices is prohibited during the 30 days prior to Screening through PTE.
- Systemic antibacterial agents potentially effective for ABSSSI are prohibited for 72 hours prior to randomization through PTE, except as rescue therapy in cases of clinical failure. A single dose of a short-acting potentially effective systemic antibacterial agent (see list in [Appendix 1](#)) administered within the 72 hours prior to randomization will be allowed for up to 25% of randomized subjects.
- Any topical antibacterial agent applied to the infection site with a spectrum that is active against the known or potential infecting pathogen(s) responsible for the infection under study within the 72 hours prior to randomization through PTE.
- MAO inhibitors. Linezolid is a reversible non-selective inhibitor of MAO. Therefore, subjects should not be enrolled who are either taking MAO inhibitors (eg, phenelzine, isocarboxazid), or have taken MAO inhibitors within 14 days prior to Screening. MAO inhibitors are prohibited from 14 days prior to Screening through the Final Follow-up assessment.
- Subjects will be instructed to avoid taking antacids and multivitamins containing multivalent cations (eg, aluminum, magnesium, calcium, bismuth, iron, or zinc) for 6 hours before and 4 hours after all odd numbered doses.

All other medications not prohibited by the protocol and considered necessary for the subject's welfare may be administered and/or continued under the supervision of the investigator.

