6.2.2 Process for Determining Inclusion in Populations

Inclusion into the ITT and Safety populations will be determined programmatically from the eCRF data. Inclusion into the CE populations will be determined programmatically from the

eCRF data and the manual review conducted by the ERT. The ERT may review subject data to confirm that population criteria are satisfied.

Inclusion into the mITT and micro-mITT population will be determined programmatically by incorporating the outcome of the review of the isolates by the ERT. The ERT will determine whether each isolate (baseline and post-baseline) is considered a pathogen based on a review of information from baseline samples including infection type, type of specimen, and local and central laboratory genus and species identification. Inclusion into the ME populations will be determined programmatically.

Review of data, Sponsor determination of evaluability, and final subject population classification will be performed in a blinded manner prior to database lock and unblinding with the exception of those criteria requiring the subject's actual treatment assignment (for example, the requirement for the subject to have received the correct test article per the randomization assignment). For the criteria requiring the subject's actual treatment assignment, population determination will be completed programmatically after unblinding.

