8.3 Handling of Missing Data

Missing data will be handled as outlined below:

- All missing and partial dates for adverse events or for medications received after randomization will be queried for a value. If no value can be obtained, substitutions will be made as detailed in [Appendix 3](#). These substitutions will be used in calculations; however, the actual value recorded on the eCRF will be used in all listings.
- Missing start and stop times for prior and concomitant antibiotics will be queried for a value. If no value can be obtained but the site indicates the antibiotic was received (onset time) prior to the first dose of test article, 00:01 will be used for the onset time. If the site also indicates that the end time was prior to the first dose of test article, 00:01 will be used for end time. The actual value (blank) will be recorded on the eCRF and will be used in the listings.
- Missing times for lesion measurements will be queried for a value. If minutes are not available, the time will be recorded to the closest hour.
- If the time of the outpatient dose of test article on Day 1 is missing, it will be imputed to 23:59.
- If no value can be obtained for all other times for events and assessments occurring after randomization, the time will not be imputed but will remain missing.
- The severity and causality assessment for adverse events cannot be missing. Missing data will be queried for a value.

For clinical and microbiological response, missing data will be handled as follows:

- For the primary outcome measure (Early Clinical Response at 48 to 72 hours):
 - The subject will be considered to have missing data if there is no lesion size measurement (either length or width) at either baseline or 46 to 72 hours after the first dose of test article. Subjects with missing data will be defined as an Indeterminate response which is essentially a Clinical Failure for the primary analysis (mITT and ITT populations).
 - If the time of administration of the first dose of test article is missing, the subject will be defined as an Indeterminate response which is essentially a Clinical Failure for the primary analysis (mITT and ITT populations).
- For the secondary outcome measures (investigator's assessment of Clinical Response at the EOT and PTE Visits):

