13.2 Prior and Concomitant Medications

All medications taken within 7 days prior to the date of informed consent through the Final Follow-up Visit will be recorded on the e-CRF. Prior medications will be summarized by WHODRUG (Version 01-Dec-2014) Anatomical Therapeutic Chemical Classification (ATC) level 3 (third level indicates the therapeutic/pharmacologic subgroup) and generic medication name. Medications are considered prior if taken prior to the first dose of test article or if their start date is unknown. Subjects will be counted only once for an ATC class and generic medication name. Concomitant medications taken during and after the study treatment period will be similarly summarized. Medications are considered concomitant if taken on or after the first dose of test article, or if their stop date is unknown or marked as continuing.

The proportion of subjects who receive the following prior and concomitant medications will be summarized by treatment group:

- Systemic and topical antibacterial medications taken within 7 days prior to first dose of test article and the reasons for receipt (mITT and CE-PTE populations)
- Systemic single dose, short-acting, non-oxazolidinone antibacterial taken within 72 hours prior to randomization
- Systemic and topical antibacterial medications (excluding test article) taken between first dose of test article and the EOT Visit (CE-EOT population) and the reasons for receipt (mITT and CE-EOT populations)
- Systemic and topical antibacterial medications (excluding test article) taken between first dose of test article and the PTE Visit (CE-PTE population) and the reasons for receipt (mITT and CE-PTE populations)
- Non-antibacterial medications taken 7 days prior to informed consent through the first dose of test article (mITT and Safety populations)

- Non-antibacterial medications taken from the first dose of test article through the Final Follow-up Visit (mITT and Safety populations)

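### The SAP's CE antibiotic windows do not meet: an isolated systemic dose, or a first topical application, between randomization and first dose does not exclude a subject from CE

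*SAP*

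**What the plan says.** **Protocol.** Section 13.1 sets one continuous period: "Systemic antibacterial agents potentially effective for ABSSSI are prohibited for 72 hours prior to randomization through PTE", apart from rescue for clinical failure and the permitted single short-acting dose before randomization. The same section prohibits active topical antibacterials on the infection site over the same period. The gap between randomization and first dose is addressed in Section 8: "Subjects should receive their first dose of test article at the site within 4 hours after randomization". That is a target, not a limit.

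**SAP, CE rules.** Section 6.1.5.2 repeats Exclusion Criterion 1, which looks back from randomization: "Has received 1 or more doses of a potentially effective systemic antibacterial treatment within the 72-hour period prior to randomization". Section 6.1.5.3 then covers "Subjects who receive any systemic concomitant antibiotic therapy from the first dose of test article through the EOT visit", and likewise through PTE for CE-PTE. For topical agents, 6.1.5.2 repeats Exclusion Criterion 2 but anchors it at first dose: "continuously within the 72-hour period prior to first dose of test article". It applies only to use of at least 72 hours. The concomitant topical rule in 6.1.5.3 also starts at first dose.

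**SAP, related text.** Section 13.2 labels by first dose: "Medications are considered prior if taken prior to the first dose of test article or if their start date is unknown". Section 10.3 makes the CE-PTE confidence interval descriptive, with no conclusion of non-inferiority. Section 7 declares no changes from the protocol analyses.

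**The concern.** The CE populations are meant to show response to test article without interference from other effective antibacterials. The protocol treats such use as prohibited throughout. The SAP enforces the prohibition in two pieces, and the pieces do not meet. A subject who receives another effective agent in the gap and then succeeds counts as an evaluable success, although the outside agent may have contributed. If such use is similar in both arms, it dilutes any true difference, and dilution favours non-inferiority.

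At stake is the definition of CE. In this SAP that touches a descriptive secondary result. For the EMA, Protocol 22.4.3 requires non-inferiority in both mITT and CE, so the wording would matter more if the EMA SAP repeats it.

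**Working it through.** **1. The windows side by side.**

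| Rule | Up to randomization | Randomization to first dose | From first dose |
|---|---|---|---|
| Protocol 13.1, systemic and topical | prohibited | prohibited | prohibited through PTE |
| SAP CE, systemic | 6.1.5.2 (72 h) | none | 6.1.5.3 |
| SAP CE, topical | 6.1.5.2, only if used for 72 h or more | 6.1.5.2, only if used for 72 h or more | 6.1.5.3 |

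A topical agent first applied in a gap planned at up to 4 hours cannot have been used for 72 hours before first dose, so the middle topical cell does not catch it.

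**2. Does another rule close the gap?** SAP 6.1.5.1 and 6.1.5.4 to 6.1.5.7 contain no antibiotic-timing rule, and 6.1.5.7 concerns criteria met before randomization. On the Evaluability Review Team, 6.2.2 says "The ERT may review subject data to confirm that population criteria are satisfied"; no power to add a criterion is stated. SAP 13.1 categorizes and tabulates prohibited-medication deviations without linking them to CE.

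**3. What is caught already.**
- A course that begins in the gap and continues past first dose is excluded under 6.1.5.3.
- If a time is missing and "the site indicates the antibiotic was received (onset time) prior to the first dose of test article, 00:01 will be used for the onset time" (8.3). That usually falls before randomization on the same day, so 6.1.5.2 applies.
- If it cannot be determined whether a stop date is after first dose, SAP Appendix 3 assumes that it is, unless the indication says otherwise. Then 6.1.5.3 applies.
- A gap dose on top of one allowed earlier dose is arguably caught, because the exception in 6.1.5.2 requires a single dose.
- An effective agent given for a different infection makes the subject a Clinical Failure at EOT (5.2.2.1.1), with no start time stated.

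What remains is an isolated systemic dose with a recorded time in the gap, given for the ABSSSI or as prophylaxis, plus the topical case.

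**4. The plan's own figures (SAP 5.1.1).** 704 × 0.80 = 563.2, stated as 564, so 564 / 2 = 282 per arm. The Farrington-Manning power per arm of n is Φ[(Δ√n − 1.96 s₀) / s₁], with s₁ = √(2p(1 − p)) and s₀ from the rates constrained to differ by Δ. For p = 0.90 and Δ = 0.10 the constrained rates are 0.8313 and 0.9313, so s₀ = 0.4519 and s₁ = 0.4243. With n = 282: (1.6793 − 1.96 × 0.4519) / 0.4243 = 1.87, giving power 96.9% (stated 97%). The same method gives 351.5 per arm for the primary endpoint, rounded up to 352, total 704 as stated.

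**5. Size.** The documents give no frequency of antibiotic use in the gap. I assume 0.3% to 1%, which is 0.003 × 282 = 0.8 to 0.01 × 282 = 2.8 subjects per CE arm.
- *Removing successes from one arm only* (no offset from the other). At 90%, 282 subjects give about 254 successes. Removing one: 254/282 = 90.07% to 253/281 = 90.04%, a change of about 0.035 points. Removing three: 251/279 = 89.96%, about 0.11 points.
- *Dilution.* If a share f succeeds in both arms regardless of treatment, the observed difference shrinks by f × d. With d as large as the 10-point margin: 0.003 × 10 = 0.03 to 0.01 × 10 = 0.1 points.
- *Power.* Removing 1% of CE (564 to 558) changes power from 96.9% to 96.8%.

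**The case against.** The strongest reply is that almost nothing is left. Continuing courses, most missing times and doses for another infection are handled, and the planned window is short. CE inclusion draws on blinded manual review, and prohibited medication is a named deviation category finalized before unblinding, so a case would probably be seen. A dose before test article cannot depend on response to it, so no imbalance between arms is expected. CE carries no non-inferiority claim in this SAP. All of this stands as a limit on importance. It does not close the gap, because seeing a case is not a stated ground for excluding it.

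Four stronger readings are tempting and not supported:
- *No antibiotic use begun in the gap excludes anyone from CE.* Too broad, given the routes in step 3 of the working.
- *Each such subject is worth 1/282 = 0.35 points.* That is the effect of turning a success into a failure. Exclusion takes the subject out of numerator and denominator, which is about a tenth of that.
- *Only the systemic rule is affected.* The first-dose anchor for topical agents helps only with use of at least 72 hours, so the topical rule has the same seam.
- *The EMA co-primary analysis is affected.* The EMA SAP is not among the documents, so its CE rules cannot be checked.

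A drafting objection also stands: starting a concomitant rule at randomization would conflict with the labels in SAP 13.2 unless the text says otherwise.

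**Conclusion.** The gap is real on the text but narrow. The SAP's CE rules are less complete than Protocol 13.1 between randomization and first dose, for an isolated systemic dose with a recorded time and for a topical agent first applied in the gap and not continued.

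The likely effect is roughly 0.03 to 0.1 percentage points on the CE rate or difference, toward no difference. This rests on an assumed 0.3% to 1% of subjects affected, the planned 282 per arm and 90% success, and, for dilution, a true difference as large as the margin. The effect on CE power is negligible. The primary mITT Early Clinical Response does not use the CE rules and is unaffected. This is a worthwhile tidy-up of a population definition, not a threat to the trial's conclusion.

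**What to change.** In SAP 6.1.5.3, start both windows at randomization: exclude for any non-study systemic antibiotic, or any topical antibacterial applied to the infection site, received from randomization through EOT (CE-EOT) or PTE (CE-PTE). Keep the present conditions on spectrum of activity, the exception for insufficient effect of test article and the exception for coated dressings. The insufficient-effect exception cannot apply to a dose before test article, so it needs no rewording. Add one sentence saying that this window applies regardless of the prior and concomitant labels in 13.2.

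This is better than extending 6.1.5.2 to first dose. That would carry the single-dose exception past randomization, whereas Protocol Appendix 1 ties it to the time before randomization.

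Check the EMA SAP for the same wording, and make any change before unblinding. The cost is one phrase and one sentence. SAP 8.3 already queries missing antibiotic times, and the prior-antibiotic listing in 9.2 already shows start and stop times and hours before randomization. Confirm that times for topical agents are recorded in the same way.
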